This is a randomized controlled trial with an active control group. Data collectors will be blinded to group assignment and because of the nature of the intervention it is not possible to blind subjects. The final sample will be 128 subjects with moderate to very severe COPD, randomly assigned to either Active-Life (experimental) or Chair-HE (active control) with blocking for COPD severity. Randomization will be performed by [name], the statistician. He will use the blockrand function from the blockrand package of the R software to generate and produce randomization cards with equal number of cases and controls. The assignments are put into sequentially numbered opaque envelopes and opened only when a patient is ready to be assigned. Active-Life and Chair-HE will be conducted in groups of 10. The Active Life groups and Chair-HE groups will be conducted separately and sessions will be scheduled so that subjects in the two groups do not meet each other. We will try to recruit enough subjects so that we can schedule 10 subjects in each group.

Outcomes will be measured at baseline; end of the structured intervention; and at 3, 6, and 12 months after completion of the intervention, total of 5 visits to measure outcomes (Figure 3). The components of the intervention and the duration of each are summarized in the table below.

[figure not shown]
The Active-Life intervention and Chair-HE include a total of 18 laboratory sessions, 11 5-minute phone coaching sessions (weekly for 2 weeks, every other week for 2 ½ months and monthly for 3 months) and 2 in-person booster sessions. Follow-up phone coaching is designed to promote long term maintenance. Staff will review PA goals and accomplishments, provide appropriate feedback to enhance self-efficacy for PA. A case report form will be completed after each interaction for purposes of documenting the intervention. Each booster session will consist of one full laboratory session with the exercise, behavioral and educational components of the experimental and/or control group interventions. The booster sessions will be performed at the 3 month and 6 month visits, immediately after the completion of all outcome measures. The experimental and control interventions will be delivered by kinesiology trained research specialists and both interventions are scripted to facilitate a systematic delivery.

Table 3. Bivariate Correlations: Social Cognitive Variables vs. Change in Physical Activity (baseline to 2 mo. follow-up, N=10)

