- Subjects must have moderate to very severe airflow limitation. The forced expiratory volume in 1 second (FEV1) compared to predicted (% predicted) must be FEV1 < 80% predicted according to GOLD standards (moderate, 50%, \leq FEV1 < 80% predicted; Severe 30% \leq FEV1 < 50%; very severe, FEV1 < 30% predicted).¹⁶⁰
- Subjects must be \geq 50 years of age,
- COPD must be their major pulmonary problem,
- can have no other major health problems that limit PA and/or walking,
- must be clinically stable at the time of enrollment,
- must be sedentary with less than 30 minutes of moderate PA 5 days a week,
- must provide written medical clearance with permission to participate in the research.

Exclusion criteria.

- People will be excluded if they have participated in a structured exercise program or pulmonary rehabilitation within the last year.
- Major health problem that limits PA
- Will be excluded if unable to meet all the above inclusion criteria.

To insure a similar severity of disease and gender mix in each group, subjects will be randomly assigned to groups that are stratified according to gender and severity of airflow obstruction (i.e., stratified randomization). Screening will include pulmonary function tests, brief history and physical exam, 6-minute walk test and permission of their physician.

Subject recruitment is one of the most challenging components of this research. We have been successful in the past and we build on this experience by establishing a multifaceted and robust plan for recruitment. Subjects will be recruited from the following sources, see letters of support.

Table 6. Recruitment location and plan pool **Size of potential subject pool**

UM Health System. We will screen medical records and mail recruitment letters to potentially qualified people. For those who respond we will conduct an initial phone screening to determine preliminary eligibility, followed by in-person screening to determine final eligibility.	1800 patients with COPD documented by pulmonary function tests

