Data Analysis Plan. Data on all patients who are randomly assigned to Active-Life intervention group and active control group will be analyzed on an intention-to-treat basis. Deviations from randomized allocation will be reported. Summary statistics will be used to characterize the sample distribution at each time period. Proper transformations will be investigated and taken if the sample distributions violate the normality assumption. For **Aim 1** of determining the Active-Life intervention effect on PA and sedentary behavior at 10 weeks, and 3, 6, and 12 months, Analysis of Covariance (ANCOVA) will be used at each time period to adjust for the baseline PA measurements and other baseline covariates.¹⁶³ The dependent variable for the ANCOVA is PA and sedentary behavior described in the Research Design section. The adjusting covariates include age, gender, COPD severity, and variables listed in the "other factors that influence PA" section. The Active-Life intervention is claimed to be effective if the marginal p -value of the intervention variable is < 0.05 . For **Aim 2** of identifying intermediate variables (or mediators) between the Active-Life intervention and PA, we will calculate the average causal mediation effects (ACME).^{164,165} The potential mediators include variables barriers-efficacy for PA, and outcome expectations for PA. The significant non-zero causal mediation effect indicates that the intervention on the PA goes through the mediator. The analysis will be carried out using the R mediation package.¹⁶⁴ Since we anticipate having missing values at 10 weeks, we plan to deal with them via standard multiple imputations. More specifically, we will run mediation analysis on multiple imputed data sets. A confidence interval is used to summarize the ACME. Finally, since the mediation analysis assumes the sequential ignorability assumption^{161,166} we will evaluate this assumption by conducting sensitivity analysis.

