Secondary Aim. To evaluate the short term and sustained effects of the Active-Life intervention, the linear mixed model (LMM) with a random intercept will be used to model the effect of the intervention. The random intercept in the LMM takes into account that the frailty indicators measured at baseline, 10 weeks; and 3, 6, and 12 months are correlated within the same individual. A number of response variables characterizing the effects of the intervention are considered, based on strength, endurance, physical function, balance, and walking speed. In addition to the binary indicator variable representing intervention or control, the demographic variables such as age, gender, and race will be added as covariates in the LMM to improve the precision of estimation. The intervention is claimed to be statistically significant if the p -value of the intervention variable is < 0.05 .

Strategies to address potential limitations.

Recruitment. We have used our state wide connections to establish a robust plan for subject recruitment. Travel distance is an important predictor of program completion,⁶³ so we will establish regional data collection sites in Grand Blanc, and Flint in addition to Ann Arbor. We require only a small space for training and all equipment is portable so all interventions and data collection can be performed on site. This will reduce the need for subjects to travel long distances for testing.

Retention activities. (a) At enrollment all subjects will be told that if they wish, they can participate in the alternative intervention after completing their assigned intervention and follow-up. This is to minimize subjects' disenchantment based on group assignment and to minimize attrition. We have taken this approach with two previous intervention studies and it dispels subjects' concerns about random assignment to groups. We will not conduct any data collection during the alternative intervention. In our experience a few people will take us up on this offer. (b) We will provide financial incentives for each data collection visit (\$25) and for each 7-days of PA data (\$50), but not for intervention visits because a financial incentive for training would limit generalizability of results. (c) To minimize the loss at follow-up, we will tell subjects that it is just as important that we study those who stop being active as those who continue with their PA.

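### The two descriptions of randomisation name different stratification factors, and the secondary-aim mixed model omits COPD severity, the factor they share; the cost is a slightly conservative test

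*Combined protocol and SAP*

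**What the plan says.** All places are in the combined protocol and SAP.

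- **Research Design** says that subjects are assigned "with blocking for COPD severity". This paragraph also gives the operational detail (software, cards, envelopes). It names no second factor.
- **Sample**, after the exclusion criteria, says that "subjects will be randomly assigned to groups that are stratified according to gender and severity of airflow obstruction", with the stated purpose of a similar mix of severity and gender in each group.
- **Data Analysis Plan, Aim 1**: "The adjusting covariates include age, gender, COPD severity", plus the variables listed as other influences on physical activity.
- **Data Analysis Plan, Secondary Aim**: "the linear mixed model (LMM) with a random intercept will be used to model the effect of the intervention", with the frailty indicators at baseline, 10 weeks, and 3, 6 and 12 months as correlated responses. On covariates, "the demographic variables such as age, gender, and race will be added as covariates in the LMM to improve the precision of estimation". COPD severity is not mentioned. The rule for a claim begins "The intervention is claimed to be statistically significant if the" and goes on to require a p-value below 0.05 for the intervention variable. No intervention-by-time term is described.
- **Table 5** places spirometry among the measures that describe the sample, not among the covariates.

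**The concern.** There are two linked issues.

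First, the plan does not state one randomisation scheme. A list restricted on severity alone and a list restricted on gender and severity are different lists, and a reader cannot tell which was generated. If it was the former, the gender balance that the Sample section aims for is left to chance.

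Second, severity is a randomisation factor under either description, yet the secondary-aim model does not contain it. Stratifying on a prognostic factor removes its contribution to the chance difference between arms. A model without that factor still counts its variance as error, so the reported standard error does not match the design. At stake is some efficiency in the frailty comparisons, in a model whose covariates are there, by the plan's own account, to gain precision.

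**Working it through.** **1. The plan's own figure.** The only sample-size figure comes from the mediation calculation in Power Analysis. With two-sided alpha 0.05, power 0.80, effect 0.26, correlation 0.3 and unit variances:

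n = (1.960 + 0.842)² / [0.26² × (1 − 0.3²)] = 7.849 / 0.0615 = 127.6, so 128.

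With 30% attrition, 128 / 0.70 = 182.9, so 183. Both figures reproduce, and neither is affected by this point. The plan gives no figure for the secondary-aim model or for the effect of stratification. What carries forward is 64 per arm and five visits.

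**2. The randomisation statements side by side.**

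| Place | Severity | Gender |
|---|---|---|
| Research Design | yes | not named |
| Sample | yes | yes |
| Aim 1 ANCOVA | adjusted | adjusted |
| Secondary-aim mixed model | not listed | adjusted |

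The inclusion criteria give three severity classes. If those classes are the strata (an assumption; the documents do not say so), severity alone gives 3 strata and gender by severity gives 2 × 3 = 6.

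**3. Effect on the test of the intervention variable.** In a random-intercept model with total variance 1, intraclass correlation ICC, five visits and 64 per arm, the model variance of the intervention main effect is

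V = [ICC × (1 − R²b) + (1 − ICC)/5] × (2/64),

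where R²b is the share of between-subject variance that severity explains beyond the covariates already in the model. Without severity, R²b = 0. Adding it therefore cuts the standard error by

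1 − √(1 − R²b × s), with s = ICC / [ICC + (1 − ICC)/5].

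The factor s enters because severity cannot reduce within-subject noise. The documents give neither ICC nor R²b, so both are assumed.

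| ICC | s | cut at R²b = 0.05 | cut at R²b = 0.15 |
|---|---|---|---|
| 0.50 | 0.5/0.60 = 0.833 | 2.1% | 6.5% |
| 0.70 | 0.7/0.76 = 0.921 | 2.3% | 7.2% |
| 0.85 | 0.85/0.88 = 0.966 | 2.4% | 7.5% |

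**4. Effect on the error rate.** If c is the ratio of the adjusted to the unadjusted standard error, the unadjusted test at nominal 0.05 has actual two-sided size 2 × [1 − Φ(1.96/c)]. An illustrative case is a severity-outcome correlation of 0.3 at a single visit with ICC 0.7, so R²b = 0.09/0.7 = 0.129 and c = √(1 − 0.129 × 0.921) = 0.939. The size is then 0.037. For an effect that would have 80% power under simple randomisation, power with stratification is 0.815 without severity in the model and 0.847 with it.

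**5. Check by simulation.** Fitted mixed models (126 subjects, three balanced strata, ICC 0.7, 60 replicates per setting) gave these mean model standard errors for the main effect:

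| correlation | without severity | with severity | cut | formula |
|---|---|---|---|---|
| 0.2 | 0.1549 | 0.1505 | 2.8% | 2.7% |
| 0.3 | 0.1549 | 0.1457 | 5.9% | 6.1% |

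The spread of the estimates across replicates was the same with and without severity, as expected when arms are balanced within strata. What changes is the reported standard error.

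**6. Intervention-by-time contrast.** In the same simulation, with baseline as a response, the standard error was 0.137 with and without severity at a correlation of 0.2. The change within a subject already removes any stable severity difference.

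**The case against.** The strongest reply has four parts.

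*The two descriptions need not conflict.* The Research Design phrase may be a short summary and the Sample section the full statement, since nothing in the former excludes gender. That stands. A reader might infer that two incompatible schemes were planned, or that gender balance was lost. The documents support neither; they support only that the scheme is not stated consistently. Even if severity alone was used, gender is balanced in expectation. With 183 enrolled and half of them women (assumed), the chance difference between arms has a standard deviation of √(0.25 × 2/91.5) = 0.074, about 7 percentage points, and gender is a covariate in both models.

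*The gain depends on the contrast.* The secondary aim speaks of short-term and sustained effects, which are most naturally intervention-by-time contrasts, and for those severity adds almost nothing. That also stands, as a condition. The text, however, bases its claim on the intervention variable and describes no interaction, and for that test the loss applies.

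*The size is assumed.* This is correct. The nearest statement in the documents, in Significance, calls the effect of severity weak to moderate, and concerns physical activity rather than frailty. If the single-visit correlation is only 0.1 to 0.2, leaving severity out inflates the standard error by 0.6 to 3.5% for ICC 0.5 to 0.85. A reader might also put 5 to 15% straight into 1 − √(1 − R²) and get 2.5 to 7.8%, but that treats the between-subject share as if it were the whole error variance.

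*The covariate list is open.* It is introduced by way of examples, but the examples are of demographic variables, and airflow severity is not one. The Measures section allows further covariates where appropriate, but that sentence concerns the influences on physical activity, and Table 5 files spirometry elsewhere. Severity is not excluded, but neither is it specified.

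**Conclusion.** The point holds as a matter of consistency and modest efficiency. The randomisation factors are stated differently in two places and need one statement. The secondary-aim model omits the one factor common to both.

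For the test as described, adding severity would cut the standard error by about 2.1 to 7.5%, assuming ICC 0.5 to 0.85, five visits, 64 per arm with complete data, and 5 to 15% of between-subject variance explained beyond age, gender and race. For an intervention-by-time contrast the gain is close to zero.

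A reader might conclude that the secondary analysis is biased or that its type I error is inflated. It is not: under stratified allocation the omission makes the test conservative. Aim 1, which already adjusts for gender and severity, and the figures of 128 and 183 are unaffected.

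**What to change.** - Add COPD severity as a fixed effect in the secondary-aim mixed model. Gender is already there, so the model then contains the factors under either description of the randomisation.
- Make the Research Design and Sample sections state the same scheme, giving the factors and their levels. If randomisation has already run, record the scheme actually used rather than choosing one afterwards.

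The cost is one model term and a sentence of protocol text. Spirometry is done at screening, so no new data are needed.

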Mastery	
Subjects complete detailed exercise logs in the laboratory.
 
 Research staff graph results and interpret for subjects to demonstrate progress. 
Exercise specialists conduct sessions and focus on progress with the following activities. Even small gains are highlighted.
 
 FCT & walking - gains in performance (level 1, 2 & 3) and the reduced effort required for a given level of training. Adherence - attendance and performance of FCT & walking, emphasizing small triumphs in overcoming barriers to adherence. Pedometers – Fitbit pedometers are used to provide objective daily feedback about the volume of walking. Fitbit data are not used to test hypotheses. 
Setting Goals: Staff will assist subjects to establish personal goals for FCT, walking and other physical activities of interest. Staff guide subjects in the development of SMART goals and provide structured feedback weekly.
 
Implementing Goals: Implementation intentions strategies – staff will assist subjects with the development of IF _____ THEN _____ statements that support the accomplishment of activity goals.
 
Staff employ cognitive rehearsal activities to assist recall and retention of gains that have been accomplished

Social modeling	
Mount large posters on the walls illustrating older people performing exercises.
 
 Illustrate that exercise and PA are enjoyable. Make the training sessions fun (music, post photographs of subjects exercising). Subjects observe their peers exercising.
Social persuasion	
Staff will frame performance feedback appropriately to enhance self-efficacy.
 
Subjects participate in a buddy system of 2-3 people who train together.
 
 Buddies train together, call each other when one does not show up for training, provide assistance and encouragement to each other as it relates to overcoming barriers to exercise and PA

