Physiological and psychological feedback system	
Staff teach subjects to understand physiological responses to exercise with an emphasis on elements unique to people with COPD.
 
 Teach subjects about how the body responds to the stress of exercising and reassure them that their responses are normal. Emphasize that muscle soreness, fatigue and dyspnea are normal responses to exercise training. Teach subjects to assess and interpret their respiratory symptoms of dyspnea and fatigue
EDUCATIONAL COMPONENTS OF ACTIVE-LIFE INTERVENTION	

PA education: Principles of exercise including individuality, specificity, progression, overload, adaptation, recovery and reversibility. Health benefits of LPA, MVPA and negative health effects of sedentary behavior and bedrest. Strategies for overcoming barriers to PA.
 
Relapse Prevention for PA:
 
 Teach subjects to differentiate between lapse, relapse and collapse. Strategies include group activities, role modeling and reflection. Structured problem solving for overcoming lapses, relapses and collapses in PA behaviors. 
Breathing Problems Action Plan: The nurse teaches subjects to assess the severity of an exacerbation and to modify their exercise accordingly. Structured problem solving includes the use of successful strategies identified by other people with COPD.
 
 Teach subjects how to modify PA during an exacerbation of COPD by maintaining frequency, decreasing intensity, increasing rest periods and decreasing the duration of exercise/PA. Teach to avoid bedrest until it is required by symptoms. Teach subjects how to re-establish PA after an exacerbation of COPD by maintaining frequency, gradually increasing intensity and gradually increasing the duration of exercise/PA. Resume PA immediately and gradually, according to ability. 	
FOLLOW-UP ACTIVITIES TO SUPPORT LONG-TERM MAINTENANCE	

 Phone coaching, 11 5-minute calls (see figure 3 for schedule) Booster sessions, 1 at 3 mo. and 1 at 6 mo. follow-up. 	

Active Control Group. Chair-HE will be performed 2/week in the laboratory and 1/week at home for 8 weeks

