Follow-up phone calls will be implemented with the same frequency as with the experimental group and focus on coaching for adherence to chair exercises and stretching. Booster session will be performed at 3 and 6 months follow-up and will include a full laboratory session with all elements.

Procedures for an intervention sessions (weeks 1 - 10)

1. Subjects arrive in the laboratory and a member of our research team (nurse, respiratory therapist or exercise specialist) measures their blood pressure, heart rate and oxygen saturation (pulse oximetry) and questions them about how they are feeling.
2. Subjects perform 20 minutes of hall walking under the direct supervision of the exercise specialist.
3. They return to the laboratory and are seated for a behavioral intervention session where the nurse or the exercise specialist leads them in a variety of activities to build their confidence in their ability to be physically active and/or delivers educational material.
4. Next subjects perform the exercises appropriate for the group assignment (Active Life group exercises together and Chair HE group exercises together). The two groups are scheduled at different times and do not come in contact with each other. This component is directly supervised by the exercise specialist. We have photos on the wall that illustrate the exercises (lab-bases exercises (photo) uploaded to section 44.1) and the exercise specialist moves around the group guiding people and giving them feedback to make sure that they are performing the exercises correctly using good form. Subjects are told to take their time as they do the exercises to minimize dyspnea.
5. The research team member measures blood pressure, heart rate and oxygen saturation (pulse oximetry) before each subject leaves the laboratory.
6. This sessions takes approximately 2 hours.

Procedures for a phone call (for additional details see coaching phone protocol in section 44.1)

1. The research staff schedule phone calls with subjects. During the phone call the staff member
 - a. assesses the extent to which a subject is meeting his/her exercise goals,
 - b. problem solves with the subject to help him/her overcome barriers to being active,
 - c. provides support and reinforces progress,
 - d. works with the subject to re-evaluate and set new goals.
2. The phone call takes approximately 5 minutes.

Procedure for booster sessions

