standard deviation of the mediator, and ρ was the correlation between the intervention and the mediator. We set type I error rate α at 0.05, type II error rate β at 0.2 (power = 0.8), the residual variance at 1, mediator variance at 1, and correlations between intervention and mediator range from 0.1 to 0.5. The effect size γ was determined using Cohen's definition of effect size from small (0.14) to medium (0.39)¹⁶². Evaluating our previous study, we expected to detect small to medium effect size ($\gamma = 0.26$). Therefore, when the correlation between the intervention variable and mediator was 0.3, we required 128 patients to reach 80% power. Because our past experience indicated 30% attrition, we proposed to enroll 183 patients at baseline to provide enough power to infer intermediate variables.

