Fidelity of the intervention. (a) All elements of the intervention and control group activities are scripted to facilitate delivery in a systematic manner. (b) We will use checklists to regularly monitor fidelity of intervention sessions and retrained staff as necessary to maintain quality. (c) We will regularly review subjects' records of laboratory activities, home-based activities, goal setting and case report forms for follow-up phone coaching. (d) We will examine uptake of the intervention by summarizing data from the self-regulation of PA scale.

Future Directions. This research advances the field by establishing a method of increasing PA that is potentially sustainable on a long-term basis. If successful next steps will be to (a) examine multiple health outcomes and (b) modify the intervention to target people with other chronic diseases, such as heart failure.

Timetable. Subject recruitment and training will be done in groups of 10. We will train new staff and recruit and enroll 40 subjects in year 1, enroll and follow-up 50 subjects/year in years 2 & 3, enroll and follow-up 43 subjects in year 4, and finish follow-up data collection, finalize data analysis and publish manuscripts in year 5.

REFERENCES

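### Training in arm-specific groups of about 10 is ignored by the Aim 1 ANCOVA and the frailty mixed model, so the p < 0.05 arm test exceeds its 5% level if outcomes correlate within groups

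*Combined protocol and SAP*

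**What the plan says.** Under Research Design, patients are assigned individually by sequential envelope. Delivery is then collective: "Active-Life and Chair-HE will be conducted in groups of 10". Ten is a target that the team will try to fill. Groups of the two arms are scheduled apart, so every training group sits inside one arm. The session procedures repeat this ("Active Life group exercises together and Chair HE group exercises together"), as does the Timetable ("Subject recruitment and training will be done in groups of 10"). The structured phase has 18 laboratory sessions.

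In Active-Life, group contact is part of the treatment. Table 4 lists watching peers exercise under social modeling, and under social persuasion it says "Subjects participate in a buddy system of 2-3 people who train together". For relapse prevention it says "Strategies include group activities, role modeling and reflection". No comparable element is described for Chair-HE.

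On analysis, the Data Analysis Plan says for Aim 1 that "Analysis of Covariance (ANCOVA) will be used at each time period to adjust for the baseline PA measurements and other baseline covariates". The covariates are age, gender, COPD severity and the listed factors that influence activity. The decision rule reads "The Active-Life intervention is claimed to be effective if the marginal" p-value of the arm variable is below 0.05. The Secondary Aim uses a linear mixed model with one random intercept, explained as covering repeated measures on the same person, and the same 0.05 rule. Neither model has a training-group term or group-robust errors, and the Power Analysis has no ICC or design effect.

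**The concern.** People who train together share staff, session times, site, season and each other. In Active-Life they are also meant to influence one another. If that leaves outcomes more alike within a training group than between groups of the same arm, patients are not independent observations. Both models treat them as independent.

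The arm estimate would remain unbiased, but its standard error would be understated. Confidence intervals for activity, sedentary time and the frailty indicators would be too narrow, and a claim of efficacy at p < 0.05 would carry more than a 5% false-positive risk. The plan in effect sets the ICC to zero without saying so, in a design that gives some reason to doubt it.

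**Working it through.** **The plan's own figure.** The Power Analysis formula with two-sided alpha 0.05, power 0.80, mediator effect 0.26, correlation 0.3 and unit variances gives n = (1.960 + 0.842)² / (0.26² × (1 − 0.3²)) = 7.849 / 0.0615 = 127.6, so 128. Allowing for 30% attrition, 128 / 0.70 = 182.9, so 183. Both reproduce, with independent observations.

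**Number and size of groups.** The Timetable enrols 40 + 50 + 50 + 43 = 183 in groups of 10, so about 18 groups, or 9 per arm. With 128 analysed, 128 / 18 is about 7 per group.

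**Aim 1 ANCOVA.** The ICC is assumed, on the baseline-adjusted outcome, with m = 7 analysed per group.
- Both arms clustered: DE = 1 + (m − 1) × ICC.
- Only Active-Life clustered: DE = 1 + (m − 1) × ICC / 2.
- Actual two-sided error = 2 × (1 − Φ(1.96 / √DE)).

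| ICC | DE, both | Type I, both | DE, Active-Life only | Type I, Active-Life only |
|---|---|---|---|---|
| 0 | 1.00 | 5.0% | 1.00 | 5.0% |
| 0.02 | 1.12 | 6.4% | 1.06 | 5.7% |
| 0.05 | 1.30 | 8.6% | 1.15 | 6.8% |
| 0.10 | 1.60 | 12.1% | 1.30 | 8.6% |

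If all 10 members were analysed (DE 1.18, 1.45, 1.90), the both-arms column would read 7.1%, 10.4% and 15.5%. If correlation were confined to Active-Life buddy sets of 2-3, error would be only 5.3-5.6% at ICC 0.05.

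A simulated ANCOVA without a group term (9 groups of 7 per arm, both arms clustered, 10,000 runs, assumed baseline correlation 0.5) rejected in 5.3%, 6.6%, 9.0% and 12.9% of null trials at ICC 0, 0.02, 0.05 and 0.10, in line with the formula. A t-test on baseline-adjusted group means with 16 degrees of freedom held 5.2-5.4% in the same runs.

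**Frailty mixed model.** With balanced visits and a patient intercept, the arm test compares patient means over five visits. Assume within-patient correlation 0.6 (patient variance 0.6, error 0.4) and a group effect on the four post-baseline visits only. The variance of a patient mean without the group effect is 0.6 + 0.4/5 = 0.68. At a single-visit ICC of 0.05, the group variance is 0.05/0.95 = 0.0526. Both arms are taken as clustered.
- Group effect identical at all four visits: contribution (4/5)² × 0.0526 = 0.0337; effective ICC 0.0337/0.7137 = 0.047; DE = 1.28; type I error 8.4%.
- Group effect unrelated from visit to visit: contribution 4 × 0.0526/25 = 0.0084; effective ICC 0.0084/0.6884 = 0.012; DE = 1.07; type I error 5.9%.

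The direction is the same as in Aim 1. The size depends on how far the group effect persists.

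**The case against.** The strongest reply is that nothing in the documents shows an ICC above zero, and several features favour a low one. Delivery is scripted and checked for fidelity, goals are personal, part of the training is at home, coaching calls are individual, and the primary outcome is seven days of free-living monitoring. Group size is only a target. The preliminary work also reports that gains in light activity in the team's earlier trial were not sustained at 12 months, so a fully persistent group effect is a high-side case. All of this stands. It limits the size and makes the point conditional, but it does not show that the ICC is zero.

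A reader might infer more than the documents support:
- **That the treatment estimate is biased.** It is not; only its standard error is affected.
- **That 128 should be multiplied by the design effect.** That number was set for the mediator coefficient ("Evaluating our previous study, we expected to detect small to medium effect size"), not for the arm contrast, and its arithmetic is correct.
- **That the mediation analysis breaks the same 5% rule.** The average causal mediation effect (ACME) is judged by a confidence interval, not an arm p-value. Its arm-to-mediator path has the same weakness, but the effect is small at low ICC. In simulation at the planned effect of 0.26, with an arm that does not move the mediator, the interval excluded zero in 3.7% of null trials at ICC 0 and 4.9% at ICC 0.02 (both arms clustered).
- **That group membership goes unrecorded.** The documents do not say so; session records are kept.

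**Conclusion.** The point holds in conditional form and should be fixed. The Aim 1 ANCOVA and the frailty mixed model omit the training group, and any positive within-group correlation takes the arm test above 5%. Confidence is high in that statement and moderate in its size.

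For Aim 1, plausible inflation runs from slight (5.7% at ICC 0.02, Active-Life only) to more than double the nominal level (12.1% at ICC 0.10, both arms). These figures rest on an assumed ICC, about 18 groups and 7 analysed per group. The frailty result also rests on the assumed within-patient correlation and on the persistence of the group effect. Whether error is in fact inflated in this trial cannot be settled from the documents; reporting the ICC would inform it.

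**What to change.** Keep a training-group identifier in the analysis data set. In the Aim 1 model, and in the frailty model with its patient intercept retained, test the arm effect with group-level or group-robust standard errors, or with a training-group random intercept. Use small-sample degrees of freedom, about 16 for 18 groups (18 − 2). Report the estimated ICC. For Aim 2, carry training group into the mediator model and the imputation model.

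The cost is SAP wording and one variable, with no extra enrolment. The price is precision in the arm contrast:
- **Group-mean analysis:** intervals about 5-6% wider at ICC 0, and about 12%, 21% and 34% wider at ICC 0.02, 0.05 and 0.10 with both arms clustered.
- **Random intercept with 16 degrees of freedom:** about 13% wider at ICC 0, and conservative (type I error 2.7-4.6% in simulation).

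Some arm-contrast power is lost. With 64 per arm, the standardized difference detectable with 80% power, 2.80 × √(2 × DE / 64), goes from 0.495 at ICC 0 to 0.524, 0.565 and 0.626 at the three ICCs (both arms, m = 7), before the small-sample correction. At a positive ICC, most of the extra width is uncertainty that the planned models leave out.
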